## 6.3 Treatment exposure and compliance

Concomitant medications/Significant non-drug therapy prior to the first dose of study treatment and after start of study treatment will be collected in the CRF, including medication name and reason. More details (including dose and dates of intake) will be provided for the following categories of treatments: osteoporosis-related medications, nutritional supplements (vitamin D/ calcium), and glucocorticoids. A Dosage administration record will be completed for each i.v. dose of ZOL/placebo. Information collected will include the date of dose, start and stop times of infusion and the reason for each dose.

Compliance with vitamin D/ calcium will be assessed by the investigator and/or study personnel at each visit using information on diet, and supplement use provided by the patient/caregiver. All study treatment and any additional treatment (i.e. vitamin D and/or calcium provided by Novartis or designee) dispensed and returned must be recorded in the Drug accountability log.

## 6.4 Efficacy

### 6.4.1 Vertebral compression fracture

At Screening, AP and lateral X-rays of the lumbar and thoracic spine will be taken to evaluate the presence of vertebral fractures of Genant grade 1 or higher or radiographic signs of vertebral compression fracture. AP spine X-ray will be employed at baseline, in order to identify fractures that may not be readily visualized on the lateral spine because of rotation/scoliosis/other.

Radiographic signs of fracture include loss of endplate parallelism, vertebral buckling and endplate interruption. Patient's eligibility must be confirmed by the central imaging laboratory before the patient can be randomized. AP and lateral thoracolumbar spine X-rays taken within 1 month of Visit 1 (screening) can be used. The film and report must be sent to central imaging for fracture confirmation.

[figure not shown]
Lateral thoracolumbar spine X-ray will also be performed at the final visit (Visit 8) to assess incident vertebral fractures. Vertebral fractures present at baseline or occurring during the study will be defined according to the Semi-Quantitative (SQ) method and confirmed with the Quantitative Morphometric (QM) method for vertebral fracture assessment:

1. Mild (Grade 1) vertebral fracture is defined as greater or equal to ( $\geq$ ) 20% and less or equal to ( $\leq$ ) 25% reduction in anterior, middle, and/or posterior vertebral height.
2. Moderate (Grade 2) vertebral fracture is defined as greater than ( $>$ ) 25% and less or equal to ( $\leq$ ) 40% reduction in any vertebral height.
3. Severe (Grade 3) vertebral fracture is defined as greater than ( $>$ ) 40% reduction in any vertebral height.

or based on radiographic signs of vertebral compression fracture including loss of endplate parallelism, vertebral buckling and endplate disruption.

Specific instructions for sending radiographic images will be distributed to investigators prior to the start of study.

Vertebral morphometry (or concave index) will be calculated using the average ratio between mid-height and posterior height from L1 to L4 ([Land et al 2006b](#))

### **6.4.3 DXA measurements**

DXA measurements of the lumbar spine (LS), total body and [REDACTED] will be performed in all patients. LS-BMD Z-score, LS bone mineral content (BMC), Total Body BMC [REDACTED] [REDACTED] will be assessed at Screening, Month 6 and Month 12. DXA will be acquired locally and the results will be sent to a central reader for evaluation. Detailed instructions will be provided in the DXA imaging manual.

#### **6.4.4 Bone Marker Analysis**

Specialized serum tests for BSAP, P1NP, TRAP-5b and NTX will be performed. Blood will be drawn from patients prior to receiving their first dose of study drug, at Month 6 and Month 12. Detailed shipping instructions will be provided in the Investigator Laboratory Manual.

#### **6.4.6 Bone age assessment**

Left posteroanterior (PA) hand/wrist X-ray will be taken at Visit 1 and at the Month 12 visit to assess bone age and the between-treatment differences for change in 2nd metacarpal cortical width at Month 12 relative to baseline.

If a fracture of the left upper extremity precludes radiographic imaging, then the right hand will be evaluated for this purpose. In this case, the right hand should be imaged at both Visit 1 and at Month 12. The information will be used in the assessment of bone density.

#### **6.4.7 Pain assessment**

Pain will be evaluated at each visit (in office and telephone visit) at randomization, Months 3, 6, 9 and 12. A FPS-R will be used for this purpose ([Appendix 4](#)).

#### **6.4.8 Appropriateness of efficacy assessments**

Fracture determination by X-ray is the standard endpoint for long-term studies in osteoporosis. However, in studies of 12 months duration, change in BMD has become an acceptable surrogate and has been shown to be a strong indicator of the efficacy of anti-resorptive therapies, including bisphosphonates such as ZOL. Bone marker assessments of change in BSAP, P1NP, TRAP-5b and NTX often parallel the change in BMD over the same time course. NTX and TRAP-5b measure bone resorption while BSAP and P1NP measure bone formation. In the growing child, [REDACTED] bone age also indicate the overall effectiveness of an intervention, but in this study, only trends may be observed over the 12 month period. Bisphosphonates are considered effective in managing bone pain, including fracture pain, and the FPS-R is a scale used to measure pain in children (Bieri et al 1990, Hicks et al 2001).

The efficacy measurements listed above are therefore expected to be appropriate for this study.

### **6.5 Safety**

#### **6.5.1 Physical examination**

Physical examination, including an oral examination of the gums and roof of the mouth, will be performed at Screening, Baseline (pre-dose, Visit 2), Month 6 and Month 12. If the investigator is concerned about the patient's oral health then the patient may be referred to a dentist.

Significant findings that are present prior to the first infusion of study drug must be included in the Relevant Medical History CRF or current medical conditions CRF. Significant findings made after the start of study drug which meet the definition of an AE must be recorded in the AE CRF.

Tanner staging will be performed at Visit 2 (baseline), Month 6 (second dose) and the end of study (EOS)/Month 12 visit.

#### **6.5.2 Vital signs**

Measurements will be made of sitting blood pressure and pulse rate at Visits 1, 2 (pre-dose), Month 6 (pre-dose) and Month 12.

Clinically notable vital signs are defined in [Appendix 1](#).

#### **6.5.3 [REDACTED] weight**

Body weight (to the nearest 0.1 kilogram (kg) in indoor clothing, but without shoes) will be performed at Visits 1, 2, Month 6 and Month 12 and recorded on the Vital sign CRF.

[REDACTED]

## 6.5.4 Laboratory evaluations

A central laboratory will be used for analysis of all specimens collected except for ionized calcium and serum creatinine (for exclusion purposes). Details on the collections, shipment of samples and reporting of results by the central laboratory are provided to investigators in the laboratory manual.

Clinically notable laboratory findings are defined in [Appendix 1](#).

EMLA cream may be used at all blood draws. EMLA Cream is a topical anesthetic which numbs the skin and decreases the sensation of pain. There should be up to three attempts to obtain a serum sample from the patient at any blood draw.

A central laboratory will collect and evaluate blood and urine samples for hematology, biochemistry and urinalysis at screening (Visit 1), Month 6 (Visit 5) and Month 12 (Visit 8).

A repeat at Visit 2 may be needed if the time between screening and Visit 2 is close to or more than 4 weeks and/or the Visit 1 result was close to the limits of the normal range.

Patients with laboratory tests containing clinically significant abnormal values will be followed regularly until the values return to normal ranges or until a valid reason for the abnormality, other than study drug related adverse event, is identified.

### 6.5.4.1 Hematology

Hemoglobin, hematocrit, red blood cell count, white blood cell count with differential counts, and platelet count will be measured.

### 6.5.4.2 Clinical chemistry

Non-fasting specimens will be obtained for glucose, creatinine, serum urea, uric acid, total protein, SGOT (AST), SGPT (ALT), alkaline phosphatase, sodium, potassium, chloride, phosphorus, magnesium, albumin, and calcium.

Specialized (non-fasting) testing for serum 25-hydroxy vitamin D will be performed at screening (Visit 1) and Month 12 (Visit 8).

Glomerular Filtration Rate (GFR) will be calculated using the Schwartz formula at all visits where serum creatinine will be measured (Visits 1, 3, 5, 6 and 8) by the central laboratory.

### Schwartz Formula to calculate Glomerular Filtration

$$\text{GFR (mL/min/1.73 m}^2\text{)} = k [\text{Height (m)}] / \text{Serum Creatinine (mg/dL)}$$

k = Constant

k=0.41

Additional renal and calcium monitoring will be performed 10 days after each study drug infusion (Visit 3 and Visit 6).

Local laboratory evaluation of serum creatinine will be performed at Visits 1 and 2, if there is an increase greater than 0.5 mg/dL (44.2  $\mu\text{mol/L}$ ), the patient should be excluded.

Serum ionized calcium will be evaluated in the local laboratory at pre-dose (first infusion). If the result is close to or below the lower limit of the normal range, the infusion must be delayed until the value has returned to normal.

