### **Status of the study as of 15-Oct-2015:**

Eighteen (18) patients have been randomized onto this study; the proposed changes will have no impact on the interpretation of the data with the exception of the definition of the evaluable (MITT) population which clarifies that patients must all have a baseline DXA (identical to ITT) and at least one post-baseline DXA.

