### **3 Investigational plan**

#### **3.1 Study design**

This will be an international, multicenter, randomized, double-blind, placebo controlled efficacy and safety study recruiting osteoporotic children and adolescents receiving glucocorticoid therapy within the 12 months preceding screening who manifest a LS-BMD Z-score of -0.5 or worse plus evidence of low impact/fragility fracture.

At the baseline visit (Visit 2), patients whose eligibility is confirmed will be randomized to one of two treatment groups. Patients may be hospitalized at the discretion of the investigator for observation following the first study drug infusion. Ionized calcium will be assessed before the first study drug infusion only. Patients will receive the second study drug infusion at the Month 6 visit. Safety and efficacy will be assessed at 6 and 12 months, with additional telephone visits to assess adverse events [REDACTED] and concomitant medication at 3 and 9 months. Renal safety utilizing the Schwartz calculation for GFR will be assessed at screening, and 10 days after the i.v. infusion of study drug 6 and 12 months.

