## 4.2 Exclusion criteria

Patients fulfilling any of the following criteria are not eligible for inclusion in this study. No additional exclusions may be applied by the investigator, in order to ensure that the study population will be representative of all eligible patients.

1. History of primary bone disease (osteogenesis imperfecta, idiopathic juvenile osteoporosis, rickets/osteomalacia).
2. Any prior use of bisphosphonates, or high dose sodium fluoride (i.e. dental use is permitted).

3. Any medical condition that might interfere with the evaluation of LS-BMD, such as severe scoliosis or spinal fusion. Patients with less than 3 evaluable vertebrae by DXA evaluation in the region of interest L1-L4, as confirmed by the central imaging laboratory, will not be considered eligible for this study.
4. As per investigator's judgment, patient is anticipated to have bone surgery within subsequent year.
5. Hypocalcemia and hypophosphatemia: any value (age-matched) below the normal range at screening.
6. Serum 25-hydroxy vitamin D concentrations of < 20 ng/mL or < 50 nmol/L at screening.
7. Renal impairment defined as an estimated glomerular filtration rate (GFR) < 60 mL/min/1.73 m^2 at screening based on the Schwartz formula at screening
8. A serum creatinine increase between Visit 1 and Visit 2 greater than 0.5 mg/dL (44.2 µmol/L).
9. Uncontrolled symptoms of cardiac failure or arrhythmia.
10. History of hyperparathyroidism or hyperthyroidism within 1 year prior to screening.
11. History of hypothyroidism unless on a stable treatment regimen for > 6 months, with at least one documented normal TSH and FT4 levels during this 6 month period.
12. History of sarcoidosis.
13. Diagnosis of active uveitis (symptomatic or asymptomatic) at the time of enrollment in the study.
14. History of hypersensitivity to any of the study drugs or its excipients or to drugs of similar chemical classes

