Patient listings will be provided for all adverse events associated with hypocalcaemia.

Laboratory parameters

The summary of laboratory evaluations will be presented with respect to three groups of laboratory tests (hematology, serum chemistry, and urinalysis).

- Hematology parameters: hemoglobin, hematocrit, red blood cell count, white blood cell count with differential counts, and platelet count.
- Serum chemistry parameters: non-fasting glucose, creatinine, serum urea, uric acid, total protein, SGOT (AST), SGPT (ALT), alkaline phosphatase, sodium, potassium, chloride, phosphorus, magnesium, albumin, calcium; and Glomerular Filtration Rate (GFR).
- Urinalysis parameters: amorphous crystals, urine bilirubin, urine blood, calcium oxalate crystals, urine color, urine glucose, urine ketone, urine leukocytes, urine nitrite, pH, urine protein dipstick, specific gravity, urine urobilinogen, and WBC Casts (Urine) /LPF.

GFR will be calculated using the Schwartz equation at all visits where serum creatinine will be measured (Visits 1, 3, 5, 6 and 8) by the Central Laboratory.

$$\text{GFR (mL/min/1.73 m}^2\text{)} = k[\text{Height (m)}]/\text{Serum Creatinine (mg/dL)}, \text{ where } k=0.41$$

Descriptive summary statistics for baseline, each post-baseline visit, and change from baseline to each visit will be presented by laboratory test group and treatment group. Note that if either the baseline or the post-baseline value is missing, then the calculation of change from baseline will also be missing.

Also, shift tables for hematology and serum chemistry will be provided in order to compare a patient's baseline laboratory evaluation relative to each study visit. For the shift tables, the normal laboratory values will be used to evaluate whether a particular laboratory test value is normal, low, or high for each visit value relative to whether or not the baseline value is normal, low, or high. These summaries will be presented by laboratory test group and treatment group.

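### As printed, the GFR formula (k = 0.41 with height in metres) cannot reach the plan's own cut-off of 60, so every child would be excluded; the likely error is a factor of 100

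*Protocol*

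**What the plan says.** Protocol 6.5.4.2 (Clinical chemistry) gives the Schwartz formula for GFR in mL/min/1.73 m² as "k [\text{Height (m)}] / \text{Serum Creatinine (mg/dL"), with the constant set to k = 0.41 on the following lines. The SAP, under Laboratory parameters, gives the same definition: "k[\text{Height (m)}]/\text{Serum Creatinine (mg/dL)}, \text{ where } k=0.41".

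The result is used in three places:

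- **Eligibility.** Protocol 4.2, criterion 7, excludes on "Renal impairment defined as an estimated glomerular filtration rate (GFR) < 60 mL/min/1.73" m² at screening and names the Schwartz formula. Footnote 1 to Table 6-1 requires the Visit 1 GFR to be available before Visit 2.
- **Renal safety.** Protocol 3.1 states: "Renal safety utilizing the Schwartz calculation for GFR will be assessed at screening, and 10 days after the i.v. infusion of study drug", and also at 6 and 12 months. Section 6.5.4.2 assigns the calculation at "Visits 1, 3, 5, 6 and 8) by the central laboratory".
- **Reporting.** The SAP lists GFR among the serum chemistry parameters, for which descriptive statistics and "change from baseline to each visit will be presented by laboratory test group and treatment group".

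Protocol Appendix 1 gives age- and sex-specific normal creatinine ranges. The lowest limit is 0.2 mg/dL and the highest is 0.9 mg/dL.

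**The concern.** The formula, its constant and the cut-off are on different scales. A child's height in metres is a number between about 1 and 2. Multiplying it by 0.41 and dividing by a creatinine of a few tenths of a mg/dL gives a result of about 1 to 4, whereas the threshold is 60.

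Two things are at stake. First, the formula is the operative definition behind an exclusion criterion for a drug that protocol 3.6 describes as capable of causing renal injury. If the printed formula was not the one applied, the documents do not record how eligibility GFRs were obtained. Second, anyone who programs or checks GFR from the protocol or SAP text would obtain wrong absolute values and wrong absolute changes from baseline.

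**Working it through.** The documents contain no worked GFR value to reproduce. The test is whether the printed formula is compatible with the plan's own cut-off.

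**Inputs**

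- GFR = k × height (m) / creatinine (mg/dL), k = 0.41: protocol 6.5.4.2 and SAP Laboratory parameters.
- Cut-off 60 mL/min/1.73 m²: protocol 4.2, criterion 7.
- Normal creatinine limits by age: protocol Appendix 1.
- Heights: not given in the visible text, so step 1 uses none and later steps use stated assumptions.

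**Step 1. Height needed to reach 60 (no height assumed)**

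Height = 60 × creatinine / 0.41.

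- At 0.2 mg/dL: 60 × 0.2 / 0.41 = 29.3 m.
- At 0.9 mg/dL: 60 × 0.9 / 0.41 = 131.7 m.

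A higher creatinine only raises the required height. Seen the other way, a child of 2.00 m would need a creatinine of 0.41 × 2.00 / 60 = 0.014 mg/dL to reach 60.

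**Step 2. Values at assumed heights**

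Lowest = 0.41 × shortest height / upper creatinine limit. Highest = 0.41 × tallest height / lower creatinine limit. The last column multiplies height by 100 and keeps k = 0.41, which is the same as k = 41 with height in metres.

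| Age (years) | Assumed height (m) | Creatinine limits used (mg/dL) | GFR as written | GFR with height in cm |
|---|---|---|---|---|
| 5–7 | 1.00–1.30 | 0.2–0.5 | 0.82–2.67 | 82–267 |
| >7–10 | 1.10–1.50 | 0.2–0.6 | 0.75–3.07 | 75–307 |
| >10–13 | 1.20–1.75 | 0.3–0.7 | 0.70–2.39 | 70–239 |
| >13–16 | 1.35–1.95 | 0.4–0.8 | 0.69–2.00 | 69–200 |
| >16–17 | 1.35–2.00 | 0.5–0.9 | 0.61–1.64 | 61–164 |

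Ignoring age bands and taking heights of 0.9 to 2.0 m, the formula as written gives 0.41 × 0.9 / 0.9 = 0.41 up to 0.41 × 2.0 / 0.2 = 4.1. Even the most favourable value falls short of 60 by a factor of 60 / 4.1 = 14.6. In centimetres the same extremes are 41 and 410. The lower one pairs a very short child with the creatinine limit for the oldest age group.

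**Step 3. A single case**

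Assumed 1.4 m and 0.5 mg/dL: 0.41 × 1.4 / 0.5 = 1.15 as written, and 0.41 × 140 / 0.5 = 114.8 with height in centimetres.

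**Step 4. Effect on change from baseline**

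Same assumed child, creatinine rising from 0.5 to 0.7 mg/dL:

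- As written: 1.148 to 0.820, a change of −0.33.
- In centimetres: 114.8 to 82.0, a change of −32.8.
- Percent change: −28.6% in both, because the factor cancels.

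**The case against.** The strongest reply is that no result is shown to be affected. The central laboratory calculates GFR, and values between 1 and 4 would be recognised at once as impossible. The status section, dated 15-Oct-2015, says "Eighteen (18) patients have been randomized onto this study", which could not have happened under the literal formula. GFR enters the SAP only as a descriptive laboratory summary with no hypothesis test, and the primary endpoint is untouched. Other renal safeguards do not use the formula: the creatinine-rise exclusion, the requirement for normal creatinine before the first infusion, the Appendix 1 creatinine limits and the search for renal adverse events by MedDRA term. All of this is correct, and it limits the severity.

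Three further qualifications are fair:

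- **The factor of 100 is inferred.** The documents alone prove only that 60 is unreachable. They do not say whether the height unit or k is wrong. Some text next to weight is blacked out (protocol 6.5.3; SAP vital signs) and may concern height, so the absence of centimetres can be asserted only for the visible text. That would not repair a formula printed in two documents.
- **The inference from the 18 children has limits.** They were randomised before Amendment 5 raised the cut-off from 35 to 60, and Amendment 3 (July 2010) had replaced an earlier version of the Schwartz formula. The cut-off of 35 is equally unreachable (35 × 0.2 / 0.41 = 17.1 m), so the inference is firm for any child screened after Amendment 3, but not for any screened before it.
- **The centimetre range depends on assumed heights.** Its floor of 61 comes from assuming 1.35 m at 0.9 mg/dL; with 1.45 m it is 66.

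A text-extraction error is unlikely, because the same pairing of metres with 0.41 stands in the protocol body, in its amendment history and in the SAP.

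**Conclusion.** The concern holds. As printed in both documents, the GFR formula cannot produce a value of 60 for any child with a creatinine at or above the lowest Appendix 1 limit, so read literally every child meets exclusion criterion 7. This conclusion needs only the documents' own formula, cut-off and creatinine limits, and that no child is 29 m tall.

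The probable size of the error is a factor of 100, consistent with a constant meant for height in centimetres. That part rests on the scale of the results at assumed heights and is not stated anywhere in the visible text. Absolute GFR values and changes computed from the text would be too small by that factor; percent changes would not be affected.

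Whether any reported GFR is wrong cannot be judged from the documents. It should be fixed because it concerns an eligibility threshold and a reported renal safety variable, but it does not bear on the primary analysis.

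**What to change.** Correct either the height unit or k in protocol 6.5.4.2 and in the SAP's Laboratory parameters section, so that the two agree with each other, with the paper on GFR estimation formulas in the protocol's reference list, and with what the central laboratory has implemented. Ask the laboratory to confirm in writing the constant and height unit behind the GFRs it has reported, including those used to judge the eligibility of children already randomised. If the confirmed formula differs from what was intended, recheck those children against criterion 7. No change to the cut-off is proposed.

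The cost is one line in each document and one query to the laboratory. Under protocol 11.1 the protocol correction needs a written amendment approved by the sponsor, the ethics committees and, where required, the health authorities; it could be bundled with another amendment. The SAP correction and the laboratory query need not wait for it.

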#### **6.5.4.3 Urinalysis**

A urine specimen will be obtained at Visits 1, 3, 5, 6 and 8 for routine urinalysis, including microscopic examination.

#### **6.5.5 Pregnancy and assessments of fertility**

Serum pregnancy tests ( $\beta$ -hCG) will be performed at screening (Visit 1) and at the final visit (Visit 8). Urine pregnancy tests will be performed at Visit 2 and Visit 5, prior to the study drug infusion. The test will be conducted for all female patients of childbearing potential. If menarche occurs during the study, a pregnancy test should be performed at the first visit following the first period.

[For sites where additional safeguards are required only due to local regulations e.g. UK, Italy, Germany, Sweden & etc., an additional supervised urine pregnancy test is required at Visit 4, 90 days after first study drug administration). In case of a positive test, the patient must contact the investigator immediately.]

